# 6.3 Subject Exclusion Criteria

- 1. Patients who are pregnant or lactating;
- 2. Chemotherapy or immunotherapy or any other anticancer therapy ≤3 weeks prior to cycle 1 day 1. Hydroxyurea may be continued until 72 hours prior to first dose and at least 24 hours before the baseline bone marrow aspiration is performed;
- 3. Major surgery within four weeks before Day 1;
- 4. Unstable cardiovascular function defined as symptomatic ischemia, uncontrolled clinically significant conduction abnormalities (ie: ventricular tachycardia on antiarrhythmics are excluded and 1st degree AV block or asymptomatic LAFB/RBBB will not be excluded), congestive heart failure (CHF) of NYHA Class ≥3, or myocardial infarction (MI) within 3 months;
- 5. Uncontrolled active infection requiring systemic antibiotics, antivirals, or antifungals within one week prior to first dose; Prophylactic antimicrobials are permitted.
- 6. Known to be HIV seropositive;
- 7. Known active hepatitis A, B, or C infection; or known to be positive for HCV RNA or HBsAg (HBV surface *antigen*);
- 8. Patients with another *active* malignancy. Asymptomatic sites of disease are not considered active. Treated or untreated sites of disease may be considered inactive if they are stable for at least 2 months and are not expected to require therapy for 4 months.
- 9. Patients with significantly diseased or obstructed gastrointestinal tract or uncontrolled vomiting or diarrhea.
- 10. Grade ≥2 peripheral neuropathy at baseline (within 21 days prior to cycle 1 day 1).
- 11. History of seizures, movement disorders or cerebrovascular accident within the past 1 years prior to cycle 1 day 1.
- 12. Patients with macular degeneration with markedly decreased visual acuity, patients with markedly decreased visual acuity (no specific etiology) or uncontrolled glaucoma.
- 13. Patients who are significantly below their ideal body weight (BMI < 17)...
- 14. Serious psychiatric or medical conditions that could interfere with treatment.

# 7.0 RECRUITMENT PLAN

Both men and women and members of all races and ethnic groups are eligible for this trial. Potential candidates for this study will be discussed during the weekly Leukemia Service new patient conference. In addition, potential study participants will be identified by a member of the patient's treatment team, the principal investigator, or research team. If the investigator is a member of the treatment team he or she will screen their patient's medical records and discuss the study with the patient. Potential study candidates identified during clinic visits or in clinical care meetings on other

services, such as the Stem Cell Transplant Service, will be referred to the principal investigator for screening and clinical management while on the study.

#### 8.1 PRETREATMENT EVALUATION

The investigator must not start any study related procedure before informed consent form is signed and dated by the patient (and impartial witness, if applicable), and investigator. The investigator is obliged to give the patient thorough information about the study and study related assessments, and the patient should be given ample time to consider his or her participation. If the screening physical exam (including vital signs, oxygen saturation) is done within five days of starting the study treatment, the exam does not need to be repeated to initiate treatment.

#### Within 30 days of starting treatment:

• Sign written informed consent

#### Within 21 days of starting treatment:

- Medical history and review of prior cancer treatment
- Review of concomitant medications
- Complete physical exam including oxygen, routine clinical neurologic examination, and visual acuity examination
- 12-lead electrocardiogram (baseline assessment)
- Routine urinalysis and microscopic exam if indicated (baseline assessment)
- Comprehensive metabolic panel, uric acid, thyroid stimulating hormone (TSH)
- Coagulation panel (PT, INR, aPTT)
- Serum pregnancy test
- Chest radiograph (baseline for subsequent comparison. If CT chest or chest X-ray done within 30-days prior to start of treatment, no chest X-ray is required)
- Opthalmalogy exam
- Bone marrow biopsy and aspirate (for baseline disease assessment and for research sample procurement)
- Baseline blood samples for exploratory pharmacodynamics assessments

#### 9.0 TREATMENT/INTERVENTION PLAN

#### 9.1. Treatment Plan

#### 9.1.1. Treatment Dose and Schedule

The starting dose of selinexor will be 60mg (PO) 2 times a week (+/- 1 day) with at least 36 hours between doses. Selinexor will be given for 2 weeks, followed by 1 week of no therapy. The scheduled dosing days should be the same days in each week. One cycle is 21 days or 4 doses (plus 1 week off). The drug administration days will occur on the same days within a cycle (ie Tue/Thu) but may be adjusted as needed from cycle to cyle. Dosing is not required to start on Day

#1 of a given cycle, which will coincide with the patient's clinic visit. Depending on patient preference for dosing days, and given the need to have results from day #1 laboratory evaluations, dosing can begin on days 1, 2, or 3 of a given cycle, but preferentially with consistency from one cycle to next.

Patients will be required to keep a drug dosing diary and symptom diary. Doses should be taken at roughly the same time of day (morning, afternoon, or evening hours), ensuring there is at least 36 hours between doses. Selinexor is taken with solid food consumption. Food should contain at least moderate fat content. Selinexor tablets should not be opened, chewed, or crushed.

Compliance to study medication will be ascertained by use of patient diaries. The date, time and number of tablets consumed will be recorded as per study drug schedule. The principal investigator or the designee will account for the number of tablets dispensed against those returned by the patient. Any deviations and missed doses will be recorded in the medical record and drug accountability logs for verification with the reasons. The investigator / designee will try to ensure complete compliance with the dosing schedule by providing timely instructions to the patients.

Dose reductions are allowed as decribed in section 9.2 (Table 1).

Patients who come off study after starting study drug because of toxicity, death, or withdrawal of consent prior to undergoing a response assessment will not be replaced and will be considered a treatment failure. Patients who enroll on study but do not receive study therapy will be replaced.

#### 9.1.2. Treatment Duration

Patients may continue on study indefinitely if they are experiencing clinical benefit, barring progression of disease, excessive toxicity,or withdrawal of consent. After discontinuation from treatment, patients will be followed by the study staff for survival status approximately evert three months.

## 9.2 Dosing Adjustments

Toxicity will be graded according to NCI CTCAE, version 4.03; the therapy modifications described below are applied according to this severity grading.

If more than one different type of toxicity occurs concurrently, the most severe grade will determine the modification.

Re-escalation of the study drug is allowed as outlined in the sections that apply for the specific toxicity. If drug-related toxicity requires a treatment delay of more than 21 days the patient is taken off protocol treatment.

Each dose modification or treatment delay must be documented, including the respective reason.

Based on observations from the ongoing Phase 1 studies in patients with advanced hematological and solid tumors, we note that selinexor shows a reasonably wide therapeutic range, with activities from ~10mg/m2 to ≥50mg/m2. Therefore, in order to optimize specific anti-tumor activity and the

patient's tolerability, we will allow for dose and/or schedule modifications as described below. Patients should also be treated aggressively with supportive care to reduce toxicities.

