# 9.2.2. Dose Modifications for Hematologic and Non-hematologic Toxicities Related to Selinexor

The criteria for dose modification for toxicities at least possibly related to selinexor are outlined below in Table 1. Supportive care guidelines for management of selinexor-related toxicities and indications for dose modifications are described in Table 2.

Table 1. Pre-specified Dose Modifications for AEs Related to Study Drug

	Dose Level		
Starting Dose	1	60mg	twice weekly
Dose Reductions	-1	40 mg	twice weekly
	-2	40 mg	once weekly

Table 2. Supportive Care and Dose Modification Guidelines

Toxicity and Intensity	Supportive treatment	Selinexor Dose Modification
Fatigue (common)		
Grade 1	Rule out other causes of fatigue. Consider addition of 4-8 mg dexamethasone or equivalent on the day after selinexor. Insure adequate caloric intake and assess volume status.	Maintain dose.
Grade 2	Rule out other causes of fatigue. Consider addition of 4-8 mg dexamethasone or equivalent on the day after selinexor. Insure adequate caloric intake and assess volume status. For additional support see NCCN fatigue guidelines.	Maintain dose. Consult medical monitor for additional option such as temporarydose reduction or short dose interruptions.
Grade 3	See above guidelines for Grade 2 fatigue	Interrupt selinexor dosing until resolved to Grade ≤ 2, For first occurrence of Grade 3, if adequate supportive care resulted in fatigue improving to Grade ≤ 1 within 7 days, restart selinexor at current dose. Otherwise, restart selinexor one dose level lower
Anorexia or Weight loss		
Grade 1	Rule out other causes of anorexia. Assess dietaryoptions (e.g., try a variety of other foods). Add high-calorie supplements (e.g., Ensure®). Consider addition of 4-8 mg dexamethasone or equivalent on the day after selinexor dosing.	Maintain dose.
Grade 2	Rule out other causes of anorexia.  Assess dietaryoptions (e.g., try a variety of other foods).  Add high-calorie supplements (e.g., Ensure®).  Consider addition of 4-8 mg dexamethasone or equivalent on the day after selinexor.  Consider megesterol acetate 80-400 mg daily.  Consider anabolic steroids such as oxandrolone, or dronabinol (Marinol®) or other cannabinoid, mainlyfor patients who cannot tolerate steroids or are at high risk to progress.  For additional supportive care see NCCN guidelines (see Appendix 8).	Selinexor may be skipped intermittently while supportive medications are instituted, usuallyfor < 1 week.

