Toxicity and Intensity	Supportive treatment	Selinexor Dose Modification
Grade 3	See guidelines for Grade 2 anorexia above	Interrupt dosing with selinexor.
		Restart selinexor at 1 dose level reduction
		(see Table 1) once anorexia resolves to Grade ≤ 2 and patient is clinicallystable.
Grade 4 (anorexia only)	See guidelines for Grade 2 anorexia above	Stop dosing of selinexor.
, ,,		Restart selinexor at 1 dose level reduction
		(see Table 1) only if anorexia resolves to
		Grade ≤ 2, patient is clinically stable other contributing factors have been addressed.
Nausea, Acute (common)		Contributing factors have been addressed.
Grade 1	Ensure adequate caloric intake and assess	Maintain dose.
	volume status.	
	Consider alternate 5-HT3 antagonists and/or D2 antagonists as needed. Consider addition of	
	NK1 antagonists.	
	Consider addition of 4-8 mg dexamethasone or	
0 1 0	equivalent on the day after selinexor.	
Grade 2	See guidelines for Grade 1 nausea above. For additional options see NCCN guidelines for	Selinexor may be skipped intermittently while supportive medications are instituted,
	antiemesis (see Appendix 7).	usuallyfor <1 week.
Grade 3	See guidelines for Grade 1 nausea.	Interrupt selinexor dosing until resolved to
	For additional options see NCCN guidelines for	Grade ≤ 2. For first occurrence of Grade 3,
	antiemesis (see Appendix 7).	if adequate supportive care resulted in nausea improve to Grade ≤ 1 within 3 days,
		restart selinexor at current dose.
		Otherwise, restart selinexor one dose level
		lower (see Table 1). If nausea stabilizes for
		at least 4 weeks at Grade ≤ 1, original dose of selinexor may be resumed.
Hyponatremia (common)		or commencer may be recumed.
Grade 1 (sodium levels <	Ensure that sodium level is corrected for	Maintain dose.
Normal to 130 nM)	hyperglycemia (serum glucose > 150 mmol/L).	
	Rule out other causes of low sodium (e.g., cardiac, hepatic, adrenal, renal and thyroid	
	diseases, SIADH, Fanconi Syndrome,	
	hyperglycemia, diuretic use).	
	Consider salt supplementation 1-2 times per	
Grade 3 (sodium levels	Ensure that sodium level is corrected for	Hold selinexor until Grade ≤ 1 (≥ 130 nM),
126-129 nM) without	hyperglycemia (serum glucose > 150 mmol/L).	restart on the same dose level.
Symptoms	Rule out other causes of low sodium (e.g.,	
	cardiac, hepatic, adrenal, renal and thyroid diseases, SIADH, Fanconi Syndrome,	
	hyperglycemia, diuretic use).	
	Initiate salt supplementation 2-3 times per day.	

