Grade 4 Thrombocytopenia Without bleeding	Follow guidelines (above) for Grade 3 thrombocytopenia without bleeding. Transfuse as per institutional guidelines.	In general, hold selinexor dos until platelet counts >50,000/mm³ or baseline, then resume selinexor dosing at one dose level lower (See Table 1). In certain cases when there is significant disease involvement in the bone marrow (e.g., in heavily pretreated multiple myeloma) or pre-existing compromised marrow function (e.g., due to prior marrow-toxic therapy), the Investigator in consultation with the Sponsor may decide to continue Selinexor dosing, provided that platelet counts and bleeding symptoms/signs are closelymonitored.
≥ Grade 3 Thrombocytopenia with bleeding	Transfuse as per institutional guidelines. Follow guidelines for Grade 3 thrombocytopenia without bleeding.	Hold selinexor dosing until platelet counts >50,000/ mm  or baseline, then resume selinexor dosing at one dose level below (See Table 1)
Neutropenia		
Grade 3 Neutropenia without fever	Implement growth factors per institutional guidelines until neutrophils are consistently > 1,500/mm  .	Maintain dose.

Toxicity and Intensity	Supportive treatment	Selinexor Dose Modification
Grade 4 Neutropenia without fever	Implement growth factors per institutional guidelines.	Reduce selinexor dose byone level (See Table 1).  After implementation of growth factors, for patients who achieve neutrophil levels > 1,500/mm³ for > 4 weeks (in the presence or absence of growth factors), selinexor dose maybe re-escalated, with frequent monitoring implemented.
Grade 3 or 4 Neutropenia with fever (febrile neutropenia)	Implement growth factors per institutional guidelines. Implement broad anti-microbial coverage per institutional guidelines. Please note that selinexor has not been associated to date with any opportunistic infections	Hold selinexor until fever resolves and patient is clinicallystable. When patient is clinically stable, restart dosing one dose level lower (See Table 1) After implementation of growth factors, for patients who achieve neutrophil levels >1,500/mm³for >4 weeks, selinexor dose may be re-escalated, provided frequent monitoring is implemented.
Other Selinexor-related A	dverse Events d	
Grade 1 or 2	Initiate standard supportive care per institutional guidelines.	Maintain dose.

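### Section 9.2 ranks concurrent toxicities by grade, but Table 2's actions do not follow grade across toxicity types, so on a plain reading Grade 4 afebrile neutropenia can displace a Grade 3 hold

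*Combined protocol and SAP*

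**What the plan says.** Section 9.2 grades toxicity by CTCAE v4.03, ties dose changes to that grade, and gives one rule for toxicities that occur together: "If more than one different type of toxicity occurs concurrently, the most severe grade will determine the modification".

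The actions for selinexor-related events are in Section 9.2.2, Table 2, in a column headed as dose modification that contains holds as well as reductions:

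- Grade 4 neutropenia without fever: "Reduce selinexor dose byone level (See Table 1"). No hold is stated. The row for "Grade 3 Neutropenia without fever" maintains the dose.
- Grade 3 fatigue: "Interrupt selinexor dosing until resolved to Grade ≤ 2, For first occurrence of Grade 3".
- Grade 3 anorexia or weight loss: "Interrupt dosing with selinexor", with restart one level lower.
- Grade 3 or higher thrombocytopenia with bleeding: "Hold selinexor dosing until platelet counts" exceed 50,000/mm³ or return to baseline, then one level lower.
- Grade 3 nausea: "Interrupt selinexor dosing until resolved to" Grade 2 or less. Grade 3 diarrhea, both Grade 3 hyponatremia rows and other related Grade 3 events also require a hold or delay.

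Section 9.2.1 holds dosing for unrelated non-hematologic toxicity of Grade 3 or higher. Section 9.2.5 waives some holds: Grade 3 nausea, vomiting or diarrhea that has not lasted beyond 3 days on adequate treatment, weight loss under 20%, alopecia, and electrolyte changes that are readily reversed.

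**The concern.** Choosing among concurrent toxicities by grade protects the patient only if a higher grade always brings an equal or stricter action. Within most single toxicities in Table 2 that is so. Across toxicities it is not, because afebrile neutropenia is handled more leniently than other events of lower grade. A patient who has Grade 3 thrombocytopenia with bleeding is held. If the same patient also has related Grade 4 afebrile neutropenia, the sentence, taken at its word, replaces the hold with a reduction, and dosing continues. A second serious toxicity should not lower the level of protection.

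Fatigue is the most relevant partner event. The dose rationale just before Section 3.5 reports that poor tolerance in this trial's first two patients was mainly due to fatigue. The grades are not given. It occurred on the earlier schedule of 8 doses per 4 weeks, and the protocol has since added a week off.

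**Working it through.** **Step 1. Apply the Section 9.2 rule to each pair.** One event is always related Grade 4 neutropenia without fever (reduce one level, no hold). The other is each Grade 3 event that has a hold of its own.

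| Concurrent Grade 3 event | Its own action | Waived by Section 9.2.5? | Plain reading of the rule |
|---|---|---|---|
| Fatigue | Interrupt | No | Reduce, keep dosing |
| Anorexia | Interrupt | No (only weight loss under 20% is) | Reduce, keep dosing |
| Thrombocytopenia with bleeding | Hold | No | Reduce, keep dosing |
| Nausea | Interrupt | Unless beyond 3 days on treatment | Conflict only if not waived |
| Diarrhea | Delay | Unless beyond 3 days on treatment | Conflict only if not waived |
| Hyponatremia (two rows) | Hold | If readily reversible | Conflict only if not waived |
| Other related events | Delay | In part (vomiting, other electrolytes, alopecia) | Conflict only if not waived |

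That gives 3 rows with no waiver and 5 with a full or partial one, 8 in all. A Table 2 footnote also spares isolated alkaline phosphatase values from the last row. By the same wording, the hold in Section 9.2.1 for an unrelated Grade 3 non-hematologic event can be displaced.

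**Step 2. Look for another rule that settles the conflict.** The note closing Table 2 bases modifications on the worst earlier toxicity but does not define worst. Section 9.2.7 requires consultation with the Principal Investigator. The calendar notes in Section 10.0 require blood-count review before cycle 1 dosing and before the first dose of each later cycle. Section 13.0 allows removal for adverse-event severity. None says which action prevails.

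**Step 3. Dose at stake (Table 1), starting dose.**

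- Starting dose: 2 × 60 = 120 mg per dosing week.
- One level lower: 2 × 40 = 80 mg; 80/120 = 67%.
- Under the fatigue, anorexia or bleeding row: 0 mg until recovery.

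**Step 4. How often Grade 4 neutropenia and Grade 3 fatigue might coincide.** The inputs are the phase 1 tables in Section 3.2. For events with rates a and b, independence gives a × b. With no assumption about dependence, the bounds are max(0, a + b − 1) and min(a, b).

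- AML cohort of KCP-330-001: a = 1/16, b = 2/16. Product 2/256 = 0.0078; × 20 = 0.16 patients. Bounds 0 and 1/16; × 20 = 0 to 1.25.
- Pooled with KCP-330-002, taking n = 50 there because 8 patients are shown as 16%. Its one neutropenia case appears to be Grade 3 with Grade 4 blank, although the table is broken in the extracted text. Grade 3 fatigue is 8. So a = (1 + 0)/66 and b = (2 + 8)/66 = 10/66. Product 10/4356 = 0.0023; × 20 = 0.05 patients. Bounds 0 and 1/66; × 20 = 0 to 0.30.

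These figures count patients who ever had each event, so truly concurrent events would be fewer. They ignore sampling error. In the AML cohort Grade 3 anorexia was 0/16, and Section 3.2 reports no bleeding with thrombocytopenia in that study, so fatigue drives the estimate for the three rows without a waiver.

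**The case against.** The best counter-argument is about wording. Section 9.2 elsewhere names dose modifications and treatment delays separately, and Section 9.2.7 does the same. On that usage the sentence fixes only the dose level and leaves every hold in force. This reading is available, and it is what a careful investigator would probably do. But no section states it, and Table 2 puts its holds in the column for dose modification, so the text supports the other reading at least as well.

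The practical safeguards also carry weight. Table 2 is titled as guidelines, this is a single-center trial, every change goes through the Principal Investigator, and blood counts are reviewed at the start of every cycle. Continued dosing through bleeding would need that consultation to let a general sentence cancel a specific hold. The bleeding hold can also end at baseline platelets, which a patient with low baseline counts may reach quickly. All of this makes harm unlikely. None of it supplies the missing rule.

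A reader might infer two further gaps. The first is equal-grade pairs, such as Grade 3 neutropenia (maintain) with Grade 3 fatigue (interrupt). Both rows are then at the highest grade, so applying both is the natural result. The second is that Grade 3 neutropenia overrides the temporary reduction for Grade 2 diarrhea; that follows from the wording but is minor. Neither adds much.

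**Conclusion.** The point stands as a patient-safety defect in one sentence. On its plain reading, Section 9.2 lets related Grade 4 afebrile neutropenia displace three Grade 3 holds outright, five more where Section 9.2.5 does not waive them, and the hold for unrelated Grade 3 non-hematologic toxicity. The consequence for one patient at the starting dose is 80 mg per dosing week where another row calls for none.

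The expected frequency is low: for the fatigue pairing, 0.05 to 0.16 of 20 patients under independence, and at most 1.25 of 20 at the AML rates without that assumption. The AML cohort is arguably closer to MDS than the solid-tumor study, but neither is an MDS population.

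Two stronger readings are not supported. The documents do not unambiguously order continued dosing, because the reading that keeps holds in force remains open. Nor does the conflict touch the primary-endpoint decision rule, the sample size or the error rates.

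**What to change.** Replace the sentence in Section 9.2 with:

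> If more than one toxicity occurs concurrently, every modification that Section 9.2 (9.2.1 to 9.2.4, including Table 2, subject to the exceptions in 9.2.5 and to the discretion that Table 2 gives for thrombocytopenia without bleeding) requires for each toxicity applies: selinexor is held if any toxicity requires a hold, until all applicable recovery criteria are met, and is then resumed at the lowest dose required by any of them.

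The rule should combine actions; choosing the single strictest one is not enough. For a first Grade 3 fatigue, "if adequate supportive care resulted in fatigue improving to Grade ≤ 1 within 7 days, restart selinexor at current dose"; asymptomatic sodium of 126 to 129 also restarts at the same level. If only the hold were kept, the neutropenia reduction would be lost and the patient would return to 120 mg per dosing week. The combined rule returns the patient to 80 mg. The scope is all of Section 9.2 because the present sentence governs unrelated toxicity, renal dysfunction and infection as well as Table 2.

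The individual actions stay as the sponsor set them. The cost is one sentence, and slightly more holds or reductions in patients with several toxicities.
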